## **5.9 Procedures and Measurements**

### **5.9.1 Inclusion/Exclusion Criteria**

All inclusion and exclusion criteria will be reviewed by the investigator or qualified designee to ensure that the subject qualifies for the trial.

### **5.9.2 Demographic Data**

Patient date of birth, race / ethnicity will be collected at screening.

### **5.9.3 Medical History**

A medical history will be obtained by the investigator or qualified designee. Medical history will include all active conditions, and any condition diagnosed within the prior 10 years that are considered to be clinically significant by the Investigator. Details regarding the disease for which the subject has enrolled in this study will be recorded separately and not listed as medical history.

### **5.9.4 Prior and Concomitant Medications Review**

#### **5.9.4.1 Prior Medications**

The investigator or qualified designee will review prior medication use, including any protocol-specified washout requirement, and record prior medication taken by the subject within 28 days before starting the trial. Treatment for the disease for which the subject has enrolled in this study will be recorded separately and not listed as a prior medication

#### **5.9.4.2 Concomitant Medications**

The investigator or qualified designee will record medication, if any, taken by the subject during the trial and 30 days after the last dose of trial treatment. All medications related to reportable SAEs and ECIs should be recorded as defined in Section 7.

The following details will be collected: drug name, reason for therapy, therapy dosage / units, frequency of therapy, route of administration, start and end date of therapy.

### **5.9.5 Disease Details and Treatments**

#### **5.9.5.1 Disease Details**

The investigator or qualified designee will obtain prior and current details regarding disease status.

#### **5.9.5.2 Prior Treatment Details**

The investigator or qualified designee will review all prior cancer treatments including systemic treatments, radiation and surgeries.

#### **5.9.5.3 Post Study Anti-Cancer Therapy Status**

The investigator or qualified designee will review all new anti-neoplastic therapy initiated after the last dose of trial treatment. If a subject initiates a new anti-cancer therapy within 30 days after the last dose of trial treatment, the 30 day Safety Follow-up visit must occur before the first dose of the new therapy. Once new anti-cancer therapy has been initiated the subject will move into survival follow-up.

CUPem	C/37/2017	Imperial College London	V7.0, 08.12.2021
-------	-----------	----------------------------	------------------

### 5.9.6 Survival Status

A record of overall survival will be made.

### 5.9.7 Adverse Events (AEs) Review

Potential new or worsening AEs will be monitored throughout the study. Refer to section 7 for detailed information regarding the assessment and recording of AEs.

### 5.9.8 Physical Examination

#### 5.9.8.1 Full Examination

A complete physical examination will be performed at screening and at other time-points, as indicated in Table 3. The following examinations should be undertaken in the complete physical examinations: general appearance, skin, head and neck, lymph nodes, thyroid, musculoskeletal/extremities, cardiovascular, respiratory, abdomen and neurological. The outcome of the examinations will be assessed as normal, abnormal (clinically significant or not clinically significant) or not done. Clinically significant abnormal findings should be recorded as medical history.

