**Table 3: Table of Assessments**

Trial Period:	Screening Phase	Treatment Cycles								End of Treatment	Post-Treatment		
Treatment Cycle/Title:	Study Screening	1	2	3	4	To be repeated beyond 8 cycles				Discon	Safety Follow-up	Follow Up Visits	Survival Follow-Up
						5	6	7	8				
Scheduling Window (Days):	-28 to -1		± 3	± 3	± 3	± 3	± 3	± 3	± 3	At time of Discon	30 days post discon	Every 8 weeks post discon	Every 12 weeks
Administrative Procedures													
Pre-screening Visit													
Informed Consent	X												
Inclusion/Exclusion Criteria	X												
Demographics and Medical History	X												
Prior and Concomitant Medication Review	X	X	X	X	X	X	X	X	X	X	X		
Trial Treatment Administration		X	X	X	X	X	X	X	X				
Trial Treatment Compliance		X	X	X	X	X	X	X	X				
Quality of Life Questionnaire (EORTC QLQ-C30)	X					X				X			
Post-study anticancer therapy status											X	X	X
Survival Status		X	X	X	X	X	X	X	X	X	X	X	X
Clinical Procedures/Assessments													
Review Adverse Events	X	X	X	X	X	X	X	X	X	X	X		
Full Physical Examination	X a	X			X				X	X	X		
Directed Physical Examination	X a	X	X	X	X	X	X	X	X	X	X	X	
Vital Signs and Weight	X a	X	X	X	X	X	X	X	X	X	X	X	
ECOG Performance Status	X a	X	X	X	X	X	X	X	X	X	X	X	
Laboratory Procedures/Assessments: analysis performed by LOCAL laboratory													
Pregnancy Test –Serum β-HCG	X b		X c		X c		X c		X c				
PT/INR and aPTT	X d	X e	X e	X e	X e	X e	X e	X e	X e	X	X	X	
CBC with Differential	X d	X e	X e	X e	X e	X e	X e	X e	X e	X	X	X	

CUPem	C/37/2017	Imperial College London	V7.0, 08.12.2021
-------	-----------	----------------------------	------------------

Trial Period:	Screening Phase	Treatment Cycles								End of Treatment	Post-Treatment		
Treatment Cycle/Title:	Study Screening	1	2	3	4	To be repeated beyond 8 cycles				Discon	Safety Follow-up	Follow Up Visits	Survival Follow-Up
						5	6	7	8				
Scheduling Window (Days):	-28 to -1		± 3	± 3	± 3	± 3	± 3	± 3	± 3	At time of Discon	30 days post discon	Every 8 weeks post discon	Every 12 weeks

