CUPem	C/37/2017	Imperial College London	V7.0, 08.12.2021
-------	-----------	----------------------------	------------------

Laboratory values that have changed significantly from baseline and are considered to be of clinical concern must be recorded as an adverse event and followed up as appropriate.

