## 7 PHARMACOVIGILANCE

### 7.1 Adverse Event (AE)

An AE is any untoward medical occurrence in a patient or clinical trial subject administered a medicinal product and which does not necessarily have a causal relationship with this treatment. An AE can therefore be any unfavourable and unintended sign (including an abnormal laboratory finding), symptom, or disease temporally associated with the use of the trial medication, whether or not considered related to the IMP.

Any worsening (i.e., any clinically significant adverse change in frequency and/or intensity) of a pre-existing condition that is temporally associated with the study treatment, is also an adverse event.

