5.6 Clinical Assessments

Physical examinations will be done at baseline and other time points to assess the general appearance, skin, head and neck, lymph nodes, thyroid, musculoskeletal/extremities, cardiovascular, respiratory, abdomen and neurological characteristics of the patient. The result of the physical examination is recorded as normal, abnormal (clinically significant or not clinically significant) or not done. Clinically significant abnormal findings should be recorded as medical history.

Vital signs including height, weight, blood pressure, body temperature, pulse and respiratory rate will be measured as indicated in assessment schedule. Vital signs may be assessed at any time during the visit; however, supine blood pressure and

pulse should be measured after 10 minutes rest. Height will be measured at initial screening visit only.

Performance status will be assessed according to ECOG (Eastern Cooperative Oncology Group) criteria as follows:

- 0 Fully active, able to carry on all pre-disease activities without restriction
- 1 Restricted in physically strenuous activity but ambulatory and able to carry out work of a light or sedentary nature. For example, light housework, office work
- 2 Ambulatory and capable of all self-care but unable to carry out any work activities. Up and about more than 50% of waking hours
- 3 Capable of only limited self-care, confined to bed or chair 50% or more of waking hours
- 4 Completely disabled. Cannot carry on any self-care. Totally confined to bed or chair
- 5 Death

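### The recording rule for physical examinations sends on-treatment findings to medical history, in conflict with the adverse event definition, and could lead to under-counting of adverse events

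*Protocol*

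**What the plan says.** On timing, Protocol 5.9.8.1 states: "A complete physical examination will be performed at screening and at other time-points, as indicated in Table 3". The section then lists the body systems and result categories and closes with the recording rule: "Clinically significant abnormal findings should be recorded as medical history". It sets no limit to screening and does not refer to Section 7.

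SAP 5.6 has the same scope, "Physical examinations will be done at baseline and other time points to assess the general appearance, skin, head and neck", and the same closing rule. The SAP does not separate full from directed examinations. In the protocol the rule stands only under the full examination.

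Elsewhere the documents say:

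- Protocol 7.1, on adverse events: "An AE can therefore be any unfavourable and unintended sign (including an abnormal laboratory finding), symptom, or disease temporally associated" with use of the trial drug. A clinically significant worsening of an existing condition also counts.
- Protocol 5.9.12, on changed laboratory values: those "considered to be of clinical concern must be recorded as an adverse event". Section 7.3 says the same of clinically important abnormal results.
- Protocol 5.9.3: "Medical history will include all active conditions, and any condition diagnosed within the prior 10 years". In Table 3 the row "Demographics and Medical History" is marked at screening only, and SAP 6.2 summarises medical history as a baseline characteristic.

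**The concern.** A clinically significant sign first seen at a post-dose examination has two destinations. The section a site consults when it performs the examination names medical history. The definition in Section 7.1 makes the sign an adverse event. A site that follows only the first commits no visible deviation, because 5.9.3 counts active conditions as medical history.

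Adverse event incidence up to 8 weeks after the last dose, overall and in PS2 patients, is the whole of the secondary objective. It bears directly on the hypothesis that pembrolizumab is tolerated far better than chemotherapy. The adverse event form captures severity, seriousness and relationship to treatment, and a sign held only as medical history would carry none of these. The examined systems include skin, thyroid, respiratory and neurological. Table 2 of the protocol itself lists thyroid disorders, pneumonitis and neurological toxicities among the drug-related events to be managed.

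**Working it through.** No sample size, power or alpha figure depends on this point. The check is a count and a comparison of text.

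**1. Which visits the rule covers.** The row "Full Physical Examination" in Table 3 is marked at screening, cycle 1, cycle 4, cycle 8, discontinuation and safety follow-up, which makes 6 visits. Protocol 3.4 places dosing after all Day 1 procedures, so the cycle 1 examination precedes the first dose. Post-dose visits: 6 − 2 = 4. Cycle 8 lies in the block of cycles that is repeated beyond 8, so patients on longer treatment have more.

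**2. Where a finding from each visit can go.**

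| Examination | Rule in 5.9.8.1 | Medical history scheduled (Table 3) | Adverse event review scheduled (Table 3) |
|---|---|---|---|
| Screening | Medical history | Yes | Yes |
| Cycle 1 (pre-dose) | Medical history | No | Yes |
| Cycle 4 | Medical history | No | Yes |
| Cycle 8 | Medical history | No | Yes |
| Discontinuation | Medical history | No | Yes |
| Safety follow-up | Medical history | No | Yes |

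The rule matches the schedule at screening only. At the four post-dose visits it names a record that is not scheduled there. The record that is scheduled there, the adverse event review, is not mentioned in the rule.

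**3. Comparison with laboratory findings.** Sections 5.9.12 and 7.3 send clinically concerning laboratory changes to the adverse event form. Examination findings have no matching sentence. Their only specific instruction points the other way.

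**4. Direction.** If a site files a new sign only as medical history, the adverse event count falls by one. If it files the sign in both places, or only as an adverse event, the count is unaffected. No route through this sentence raises the count, so any error is towards under-counting.

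**5. Scale.** The documents give no rate of new examination findings, so the expected number misfiled cannot be calculated. For orientation only, assume that all enrolled patients are dosed and that the final number lies in the planned range of 31 to 67. One patient whose sign is misfiled then lowers the patient-level incidence of that particular event by between 1/67 = 1.5 and 1/31 = 3.2 percentage points. The incidence of any adverse event moves only if that patient has no other event recorded. The step is larger in the PS2 subset, whose size the documents do not state.

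**The case against.** The strongest reply is that adverse event capture is already required at these visits. Section 5.9.7, just before the examination section, monitors new or worsening events throughout and refers to Section 7. Section 7.2 collects events from consent to the safety visit. Table 3 schedules an adverse event review at every visit that has a full examination. A new rash at cycle 4 is an adverse event under Section 7 whatever else is written down, and a site may record both. The screening-only mark for medical history also suggests that the sentence was meant for baseline.

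Much of this stands. A reader might infer that the plan tells sites to use medical history in place of the adverse event form, so that new signs drop out of the endpoint. The text does not say that. No section exempts examination signs from adverse event recording, and loss requires a site both to follow the examination sentence and to omit the event.

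A reader might also infer that adverse event incidence is the only tolerability evidence. It is not. SAP 6.5 and 6.11 also plan tables of serious adverse events, laboratory values, vital signs and ECOG status. The sentence does not touch reported symptoms. Signs unequivocally due to progression are excluded from adverse events in any case by Section 7.1.1, and in metastatic disease some new signs will fall there.

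The reply does not remove the contradiction. The general rule and the specific instruction disagree, the specific one lacks a cross-reference to Section 7, and it appears in both documents.

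**Conclusion.** The instruction is wrong as written for examinations after screening and conflicts with Section 7.1, Table 3 and the laboratory rule. It affects four of the six scheduled full examinations, plus any repeats beyond cycle 8. The consequence is a risk of incomplete or inconsistent capture of new or worsened signs, and any bias runs towards a lower adverse event incidence. Its size cannot be derived, and it depends on how sites read the sentence.

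This is of moderate importance. It concerns the secondary endpoint and is worth correcting, but it does not alter the primary endpoints, the sample size or the analysis methods.

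**What to change.** Replace the sentence in Protocol 5.9.8.1 and in SAP 5.6 with wording such as:

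*An abnormality judged clinically significant at the screening examination, with onset before consent, is entered as medical history. An abnormality at any examination that is new or has worsened since consent, meets the Section 7.1 definition and is not unequivocally due to disease progression (Section 7.1.1) is recorded as an adverse event under Section 7.2.*

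The progression clause is needed so that the new sentence does not contradict 7.1.1.

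Before database lock, query medical-history entries whose onset date is after consent, and have the investigator assess each against 7.1 and 7.1.1 for the adverse event form. The query should use onset date and not entry date: screening follows consent, so a query on entry date would also pick up legitimate baseline history. Entries should be assessed individually and not transferred wholesale, since some will be signs of progression.

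The cost is one passage of text in each document, a one-off data check, and possibly a slightly higher reported adverse event rate.

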#### 5.9.8.2 Direct Examination

For cycles that do not require a full physical exam as indicated in Table 3, a directed physical exam will be performed as clinically indicated prior to trial treatment administration.

During the COVID-19 pandemic, this can be omitted if the risk of COVID-19 is higher than omitting the examination however, this should be conducted should other study assessments reveal the need for one.

### 5.9.9 Vital Signs and Weight

Vital signs including height, weight, blood pressure, body temperature, pulse and respiratory rate will be measured as indicated in Table 3. Vital signs may be assessed at any time during the visit; however, supine blood pressure and pulse should be measured after 10 minutes rest. Height will be measured at initial screening visit only.

### 5.9.10 ECOG Performance Status

Performance status will be assessed as indicated in Table 3 according to ECOG criteria as follows:

**Table 4: ECOG Performance Status**

0	Fully active, able to carry on all pre-disease activities without restriction
1	Restricted in physically strenuous activity but ambulatory and able to carry out work of a light or sedentary nature. For example, light housework, office work
2	Ambulatory and capable of all self-care but unable to carry out any work activities. Up and about more than 50% of waking hours
3	Capable of only limited self-care, confined to bed or chair 50% or more of waking hours
4	Completely disabled. Cannot carry on any self-care. Totally confined to bed or chair

CUPem	C/37/2017	Imperial College London	V7.0, 08.12.2021
-------	-----------	----------------------------	------------------

5	Death
---	-------

### 5.9.11 Pregnancy Tests

A blood serum pregnancy test will be performed for women of childbearing potential at screening. In patients of childbearing potential, a urine pregnancy test must be performed prior to study treatment on Day 1 of every cycle with negative results available before study treatment is administered. A blood serum pregnancy test may be performed within 3 days prior to study treatment in place of the Day 1 urine test.

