### **5.3 Treatment Period**

Patients will receive their study treatment until disease progression, unacceptable toxicity or withdrawal. Patients will be required to attend clinic for assessments to be performed during treatment as per Table of Assessments (Table 3).

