## 5.8 Study Schedules during Treatment

Table 3 summarizes the trial procedures to be performed at each visit. Individual trial procedures are described in detail below. Treatment is divided into cycles of 21 days, with visits and assessments specified according to the relevant cycle.

Unless otherwise indicated, scheduled assessments may take place within  $\pm 3$  days of the specified visit. Assessment days are relative to the start of study treatment i.e. Cycle 1 Day 1.

If a patient has a treatment break, please contact the Clinical Trials Section (CTS) for advice regarding the timing of research blood assessments. All other assessments, including laboratory safety assessments, vital signs and radiological imaging should continue to be performed.

CUPem	C/37/2017	Imperial College London	V7.0; 08.12.2021
-------	-----------	----------------------------	------------------

Furthermore, additional evaluations/testing may be deemed necessary by the Sponsor and/or MSD for reasons related to subject safety. In some cases, such evaluation/testing may be potentially sensitive in nature (e.g., HIV, Hepatitis C, etc.), and thus local regulations may require that additional informed consent be obtained from the subject. In these cases, such evaluations/testing will be performed in accordance with those regulations.

**During the COVID-19 pandemic, patients whom are under ongoing treatment can be offered longer intervals of 1 to 2 weeks between treatment to avoid peak COVID-19 capacity issues.**

CUPem	C/37/2017	Imperial College London	V7.0; 08.12.2021
-------	-----------	----------------------------	------------------

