Comprehensive Serum Chemistry Panel including full or directed tumor marker panel (+/- NET serum markers)	X d	x e	X e	X e	X e	X e	X e	X e	X e	X	X		
Urinalysis	X d	X e	X e	X e	X e	X e	X e	X e	X e	X	X		
T3, FT4 and TSH	X d	x e	X e	X e	X e	X e	X e	X e	X e	X	X	X	
Efficacy Measurements													
Tumor Imaging	X f					X g			X	X (if not done within 12 weeks prior)		X	
Tumor Biopsies/Archival Tissue Collection/Correlative Studies Blood													
Archival or Newly Obtained Tissue Collection	X h												
Correlative Studies Blood & Urine Collection	X		X		X		X		X	X	X		

CUPem	C/37/2017	Imperial College London	V7.0, 08.12.2021
-------	-----------	----------------------------	------------------

Trial Period:	Screening Phase	Treatment Cycles								End of Treatment	Post-Treatment		
Treatment Cycle/Title:	Study Screening	1	2	3	4	To be repeated beyond 8 cycles				Discon	Safety Follow-up	Follow Up Visits	Survival Follow-Up
Scheduling Window (Days):	-28 to -1		± 3	± 3	± 3	± 3	± 3	± 3	± 3	At time of Discon	30 days post discon	Every 8 weeks post discon	Every 12 weeks
a In circumstances where screening assessments are conducted within 3 days prior to treatment initiation these can be used to cover both screening and C1D1.													
b Mandatory negative blood serum pregnancy test at screening for patients of childbearing potential.													
c In patients of childbearing potential: 
 
• Mandatory negative serum pregnancy test within 72 hours prior to receiving study treatment
 
• Mandatory negative urine pregnancy test result available prior to receiving study treatment
 
													
d Lab tests (blood samples for haematology, clinical chemistry and urinalysis) for screening should be performed within 10 days prior to the first dose of treatment. In circumstances where blood samples for haematology and clinical chemistry and urinalysis fulfils both the timeline of day -10 to 0 and 72 hours prior to C1D1 dosing these can be used for both screening and C1D1.													

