### 5.9.12 Laboratory Evaluations

Blood samples for haematology and clinical chemistry and urinalysis will be taken at scheduled visits and analysed at the local laboratory using standard methods for routine tests. **NB. Laboratory tests for screening or entry into the trial should be performed within 10 days prior to the first dose of treatment, on dosing days for all cycles, samples must be taken pre-dose (up to 72 hours prior to dosing).** Samples must be processed, and results available, prior to study treatment administration to ensure and confirm an assessment of patient suitability. In circumstances where blood samples for haematology and clinical chemistry and urinalysis fulfils both the timeline of day -10 to 0 and 72 hours prior to C1D1 dosing these can be used to cover both screening and C1D1.

The following variables will be measured at the time-points indicated in Table 3.

- Biochemistry: Sodium [Na], potassium [K], chloride [Cl], bicarbonate [CO2]‡, Uric Acid, calcium, phosphate, glucose), Alanine aminotransferase (ALT), Aspartate aminotransferase (AST), alkaline phosphatase, albumin, Lactate dehydrogenase (LDH), total bilirubin, direct bilirubin (*If total bilirubin is elevated above the upper limit of normal*), total protein, magnesium
- Haematology: White blood cell count (WBC) with differential (to include neutrophils, lymphocytes, monocytes, eosinophils, basophils), red blood cell (RBC) count haemoglobin (Hgb), haematocrit (Hct), Absolute neutrophil count (ANC), Absolute lymphocyte count (ALC) and platelet count.
- Coagulation: PT/INR and aPTT
- Urinalysis: Macroscopic assessment of the amount of protein, glucose, white blood cells and blood if they are present (levels should be recorded if available) and microscopic analysis should be performed if an abnormality is noted.
- Pregnancy test for patients of child-bearing potential (***If urine pregnancy results cannot be confirmed as negative, a serum pregnancy test will be required.*** Serum  $\beta$ -human chorionic gonadotropin ( $\beta$ -hCG) for patients of child-bearing potential
- Thyroid: Total triiodothyronine (T3), Free thyroxine (FT4), Thyroid stimulating hormone (TSH)
- Tumour Markers for CUP +/- any serum markers deemed to be relevant to disease monitoring, e.g. PSA, b-HCG, CEA, Ca19.9, Ca125, Ca153, AFP, NSE, SCC, S100, and Chromogranin A and B.
- ‡ *If considered standard of care in your region.*

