#### **5.9.17 Research Blood and Urine Samples**

Research bloods and urine sample for this study are optional, and are as follows:

- Correlative translational study samples (blood and serum) will be collected at screening, cycle 2 and then every other cycle, at end of treatment and then at safety follow up visit. The samples will be banked for retrospective immune-modulating and other biomarkers.
- Serum and urinary metabolomic profiling – at screening, cycle 2 and then every other cycle, at end of treatment and then at safety follow up visit. H NMR Global Metabolic Phenotyping followed by validation using mass spectrometry (LC-MS) will be carried out in house taking advantage of the Imperial College expertise within the National Phenome Centre. This sub-project is already running within the cancer department at Imperial for many tumour types. In this context, metabolomic profiling will be looked at in the context of responders to Pembrolizumab.

The date of collection and sample IDs will be recorded on the eCRF.

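### The protocol text requires a negative pregnancy test before every dose, but the assessment schedule marks none at cycles 3, 5, 7 and later odd cycles

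*Protocol*

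**What the plan says.** Protocol section 5.9.11 sets the rule for patients of childbearing potential: "a urine pregnancy test must be performed prior to study treatment on Day 1 of every cycle". The negative result must be in hand before the drug is given, and a serum test in the 3 days before dosing may stand in for the urine test.

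Table 3 has a single pregnancy row, "Pregnancy Test –Serum β-HCG", with marks at screening and cycles 2, 4, 6 and 8. Treatment administration is marked at all eight cycles. The header says the block of cycles 5 to 8 repeats for later cycles. Footnote c, attached to the even-cycle marks only, has two bullets: "Mandatory negative serum pregnancy test within 72 hours prior to receiving study treatment" and "Mandatory negative urine pregnancy test result available prior to receiving study treatment". SAP Table 2 repeats the row and the footnote.

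Section 5.8 describes the table's role: "Table 3 summarizes the trial procedures to be performed at each visit". Section 5.3 has patients attend clinic for "assessments to be performed during treatment as per Table of Assessments (Table 3"). Section 5.9.12, whose list includes the pregnancy test, opens with "The following variables will be measured at the time-points indicated in Table 3". Section 3.4 makes dosing follow completion of the procedures in the Table of Assessments.

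**The concern.** Two current parts of the protocol give different schedules for a mandatory pre-dose safety test. Section 5.9.11 asks for it before every dose; the table that sites are told to work from shows it before every second dose. A site that builds its visit checklist from Table 3 could give cycle 3 without a test, satisfy the table, and breach section 5.9.11.

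The two places also differ on which test is needed. Footnote c lists serum and urine as separate mandatory items, while section 5.9.11 accepts either, as does section 5.6 before retreatment. A site that takes footnote c literally runs two tests where the text asks for one.

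Section 6.9.2 warns that pembrolizumab may harm a foetus. Sections 6.9.2 and 6.9.3 require contraception and removal from the study on pregnancy, which limits the harm. Removal depends on the pregnancy being detected, however, and detection is the purpose of the test.

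**Working it through.** The plan states no figure to reproduce. The check compares the text with the table and then counts doses.

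**1. Reading the table row.** The risk with a table extracted from PDF is that marks shift between columns. The correlative blood and urine row in Table 3 carries the same cycle marks as the pregnancy row, and section 5.9.17 describes that schedule in words: samples "will be collected at screening, cycle 2 and then every other cycle". The even-cycle reading is therefore sound, and the same row appears in SAP Table 2.

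**2. Text against table.**

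| Cycle | 1 | 2 | 3 | 4 | 5 | 6 | 7 | 8 |
|---|---|---|---|---|---|---|---|---|
| Dose given | yes | yes | yes | yes | yes | yes | yes | yes |
| Test required by section 5.9.11 | yes | yes | yes | yes | yes | yes | yes | yes |
| Test marked in Table 3 | no | yes | no | yes | no | yes | no | yes |

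Cycle 1 is not a gap: inclusion criterion 8 requires a negative serum test within 72 hours before the first dose. That leaves cycles 3, 5 and 7, which is 3 of the 8 displayed. Repeating the cycle 5–8 block maps cycles 9 and 11 to the blank columns 5 and 7, so later odd cycles are unmarked too.

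**3. Interval.** Cycles last 21 days. Marks at every second cycle are 2 × 21 = 42 days apart, against the 21 days that the text implies.

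**4. Doses per patient.** Assumption: dosing every 21 days from day 0, stopping at progression, with progression at the planning PFS medians in section 8.2 (2 and 4 months). The number of doses is the whole part of (days ÷ 21), plus 1.

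- 2 months: 2 × 365.25 ÷ 12 = 60.9 days; 60.9 ÷ 21 = 2.9; 2 + 1 = 3 doses. Unmarked: cycle 3, so 1 dose.
- 4 months: 4 × 365.25 ÷ 12 = 121.8 days; 121.8 ÷ 21 = 5.8; 5 + 1 = 6 doses. Unmarked: cycles 3 and 5, so 2 doses.

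**5. Long treatment.** For a patient who receives 35 doses, the unmarked cycles are 3, 5, …, 35, which is (35 − 3) ÷ 2 + 1 = 17. This is not a ceiling: section 6.9.6 takes the later of 24 months and 35 administrations, and section 5.6 allows up to a further year.

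**The case against.** The strongest reply is that the rule is already in the protocol. Section 5.8 calls Table 3 a summary and says that the individual procedures are described afterwards; section 5.9.11 is that description, and it is explicit. The row is also labelled serum, whereas the every-cycle test is a urine test, so the row could be read as a separate serum schedule that leaves the urine rule intact.

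The first part stands to this extent: the safeguard is not missing, and nothing in the documents shows that a test has been missed. It does not remove the conflict, because sections 3.4, 5.3 and 5.9.12 all send sites to the table and the documents supplied give no rule that text prevails over table. The serum-only reading leaves the urine test with no row at all, and footnote c ties the urine test to the even-cycle cells.

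On the two-test point, section 5.9.12 adds that serum is required when a urine result cannot be confirmed as negative. That suggests urine first and serum as back-up, but it does not reconcile a footnote listing both as mandatory with a text that accepts either.

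The dose range can fairly be called rough, since it stops dosing on the day of progression. Scheduled scans are 12-weekly. If progression is found only at the next scan, the counts become 84 ÷ 21 = 4 doses before day 84 (cycle 3 unmarked) and 168 ÷ 21 = 8 doses before day 168 (cycles 3, 5 and 7 unmarked). Earlier clinical progression would shorten this; treatment beyond first progression would lengthen it. On the scan-based reading, the 1-to-2 figure understates the gap.

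**Conclusion.** The inconsistency is real and should be corrected. Table 3 omits a mandatory pre-dose test at 3 of the 8 displayed cycles and at every later odd cycle, doubling the interval between scheduled tests from 21 to 42 days. On the day-of-progression assumption this is 1 to 2 doses per patient at the planning medians, and 17 for a patient who receives 35 doses. The cycle count and the interval follow directly from the documents. The per-patient figures rest on whole-cohort planning medians, which may not describe patients of childbearing potential. Because the number of such patients is not given, total exposure cannot be estimated. The correct rule already exists in section 5.9.11, so this is a defect in the operating schedule. It bears on patient safety only; the design, endpoints and efficacy analyses are unaffected.

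**What to change.** Make Table 3 follow section 5.9.11:

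- Mark the pregnancy test at every cycle, including cycles beyond 8, and relabel the row as urine or serum.
- Reword footnote c to require, before each dose, either a negative urine test on Day 1 or a negative serum test within the preceding 72 hours. The back-up serum rule in section 5.9.12 can stay as it is.
- Add criterion 8's 72-hour serum limit to footnote b or to the cycle 1 cell. This closes no gap, but it lets a site working from the table see the first-dose rule.
- Copy the corrected row and footnotes into SAP Table 2.

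The cost is an edit to one table row and two footnotes in the protocol, repeated in the SAP. A site now working from the table would do one more urine test at each odd cycle after the first for patients of childbearing potential. Section 5.9.11 already requires that test, so the protocol's overall burden does not rise.
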